NCT03705273

Randomized controlled trial of dexamethasone
oral preparations to assess palatability and adverse effects
in children with asthma and croup

Protocol Date: 09.19.2018

Study Description and Protocol

Principal Investigator:
[name], MPH
Pediatric Emergency Medicine

Co-investigators
[name].
Pediatric Pharmacy Resident

[name]., BCPPS
Pediatric Clinical Pharmacist

[name]., BCPS, BCPPS
Pediatric Clinical Pharmacist

Vanderbilt Children's Hospital
[name]
[name]

09.19.18

I. Specific Aim and Study Hypothesis

Specific Aim: To examine the palatability and acceptability of oral dexamethasone tablets crushed in apple sauce or pudding in comparison with the IV solution mixed with sugar syrup.

Hypothesis: We hypothesize that dexamethasone tablets crushed and administered in apple sauce or pudding at a dose of 0.6 mg/kg will be more palatable and acceptable in comparison to the IV form of the drug mixed in sugar syrup, for acute asthma exacerbations or croup in children aged 1 – 7 years in a pediatric emergency department.

II. Summary of Approach

To address the Specific Aim we will conduct a 2-arm RCT of dexamethasone tablets crushed in apple sauce or pudding in comparison to the current approach in the VCH ED, dexamethasone IV solution mixed in sugar syrup. The outcome, palatability and acceptability, will be assessed using a smiley-face analog scale and questionnaire that will be completed by the participant's parent 1-hour after administration of dexamethasone.

Treatment allocation (randomization) will be determined by a pre-determined randomization sequence in randomly-permuted blocks of 4, to be generated using Stata statistical software. Envelopes containing treatment allocation by sequential participant ID will be in the VCH-ED charting room where physicians and nurse practitioners enter orders for this medication in Epic. When a parent and patient provide consent/assent, the next envelope will be opened to determine treatment allocation. The clinician will then enter the order for dexamethasone tablets or IV solution in accordance with this. The clinician will ask the participant's parent to complete the data collection form (enclosed with this application) 1-hour after medication administration.

Treatment allocation cannot be blinded because the vehicle (apple sauce, pudding or sugar syrup) may be associated with palatability and acceptability.

III. Background

Asthma is the most prevalent chronic serious disease of childhood and the most frequent reason for childhood hospitalization in the United States. Asthma and croup are common patient diagnoses in the pediatric emergency department, and national guidelines recommend oral dexamethasone (a corticosteroid) as a fundamental treatment for both conditions. Dexamethasone is the preferred corticosteroid because the duration of clinical effect is 2-3 days, a period sufficient to treat these conditions. The current dexamethasone preparation used at VCH is the intravenous (IV) preparation mixed with cherry syrup. Our nursing staff prefers this preparation. However, some children spit this preparation out or have vomiting afterward.

IV. Inclusion and Exclusion Criteria

a. Inclusion criteria

- i. Diagnosis of acute asthma exacerbation or croup (laryngotracheitis) in the VCH ED
- ii. Age 1 to 7 years
- iii. Dexamethasone treatment indicated
- iv. No other acute or chronic process accounting for signs and symptoms (e.g., foreign body aspiration, pneumonia, cystic fibrosis)
- v. Have not received systemic corticosteroid for current episode prior to enrollment

b. Exclusion criteria

- i. Allergy to dexamethasone or apple sauce and pudding
- ii. Unable to take medication orally

V. Subject Recruitment and Enrollment

We will enroll a convenience sample of 220 children 1-7 years of age and their parent, who will provide secondary data on their child. The investigators will be clinicians (attending physicians, fellows, pharmacists, nurses, or nurse practitioners) caring for patients in the VCH ED and will identify patients presenting with signs (e.g., tachypnea, wheezing, accessory muscle use) and symptoms (e.g., respiratory distress, dyspnea, cough,) consistent with an asthma exacerbation or croup (barky cough, inspiratory stridor).

The investigator will seek written informed consent from the parent and verbal assent from the child. If these are provided, the patient will be enrolled as a participant. Based on the proposed sample size described in a later section of the protocol, we anticipate enrollment of 220 patients and 220 parents.

VI. Study Procedures

Study Design

The study design will be an RCT with randomization in randomly-permuted blocks of four. After participant enrollment and ascertainment of treatment allocation (randomization), the clinician will order dexamethasone accordingly in tablet or IV form. The investigator will provide the parent with the study data form and instruct the parent in completion of this form 1-hour after dexamethasone administration.

VII. Predictor Variables

The predictor variable will be treatment-allocation (dexamethasone tablet or IV preparation administered orally).

VIII. Outcome Variables

The outcome variable will be palatability as defined by a 5-point "smiley-face" visual analog scale that the parent will complete on the study data form. Secondary outcomes will include emesis; need to re-administer the medication, need to provide alternate vehicle for medication (e.g., intravenous or intramuscular).

IX. Ethical Considerations

Systemic corticosteroid is a fundamental component of treatment for acute asthma exacerbations and croup, and dexamethasone has been identified at VCH and nationally as the optimal systemic corticosteroid for these children. The IV form of dexamethasone is used currently at VCH and in most pediatric ED's nationally. However, previous research has demonstrated that dexamethasone tablets are better tolerated than prednisolone (a different corticosteroid) syrup. There is equipoise whether dexamethasone as the IV form or tablet is more palatable and acceptable to these children, and this research seeks to answer the important question whether we should be using the tablets.

X. Risks of Study Participation

The risk to participants is not increased over current practice pertaining to administration of dexamethasone orally. The IV form is currently in use, and the tablets are widely acknowledged to be well tolerated by children. However, any apparent adverse events (e.g., allergy to apple sauce or pudding) will be reported by the investigators to [name] who will immediately inform the IRB as noted below.

XI. Reporting of Adverse Events or Unanticipated Problems Involving Risk to Subjects or Others

Any unexpected problems involving risks to subjects or others will be immediately reported to the Institutional Review Board of Vanderbilt University within ten days using the IRB form #1105.

XII. Study Withdrawal or Discontinuation

We are taking several measures to ensure that there is a clear distinction for the patient and parent/guardian(s) between clinical care and the research data collection for this investigation. Patients and their parent/guardian(s) will be told very explicitly by the investigators that their participation in this research investigation is entirely voluntary and that they may withdraw at any time. We will further emphasize verbally and in the informed consent document that a decision on the part of the patient or parent/guardian(s) to not participate will in no way change, compromise or jeopardize the patient's care. Indeed, we anticipate that some eligible patients will not be enrolled on this basis.

XIII. Data Management

A *Subject Data Form* will be used for data acquisition. All data will be entered in a secure REDCap database. This data will then be entered into Stata® (v.8, College Station, TX) for statistical analysis.

XIV. Clinicaltrials.gov registration: Pending

XV. Statistical Considerations

We will examine palatability using the 5-point analog ("smiley-face") scale and will ask the parent to make a mark on this scale. This mark will be used to estimate palatability as a continuous variable (e.g., 5.6 cm).

XVI. Sample Size

In a cohort of children aged 2 – 10 years who received oral dexamethasone as the elixir and using a 5-point Hedonic scale ("smiley-face" scale) was used to assess palatability,¹ Aljebab and colleagues reported a mean value for palatability of 3 with SD 1.1. If the true, mean difference between dexamethasone tablet and IV solution administered orally is 0.5, we will need to study 103 experimental subjects and 103 control subjects to be able to reject the null hypothesis that the population means of the experimental and control groups are equal with probability (power) 0.9. The Type I error probability associated with this test of this null hypothesis is 0.05.

With the above in mind, we propose to enroll 110 participants in each treatment-allocation arm of this RCT to account for dropouts and missing data.

XVII. Privacy and Confidentiality Issues

After the parents have signed the consent, one copy will be given to the parents and one copy will be kept by [name] in his office. All efforts, within reason, will be made to keep protected health information (PHI) private. PHI is health information that is or has been gathered or kept by Vanderbilt as a result of a subject's healthcare. This includes data gathered for research studies and can be traced back to the subject. Using or sharing ("disclosure") such data must follow federal privacy rules. By signing the consent for this study, subjects are agreeing ("authorization") to the uses and likely sharing of PHI. If a patient decides to be in this research study, he/she is also agreeing to let the study team use and share PHI as described below.

As part of the study, [name] and his study team may share the results of a subjects' study and/or non-study linked lab tests, as well as parts of the medical record, to the groups named below. These groups may include people from the Federal Government Office for Human Research Protections, the Vanderbilt University Institutional Review Board. Federal privacy rules may not apply to these groups; they have their own rules and codes to assure that all efforts, within reason, will be made to keep PHI private. [name] may give health data, without a subject's name, to others or use it for other research projects. Vanderbilt and [name] and his staff will keep each subject's PHI in strict confidence, and will comply with any and all laws regarding the privacy of such information.

The study results will be kept in the subject's research record for at least six years after the study is finished. At that time, the research data that has not been put in the subject's medical record will be destroyed. Any research data that has been put into the medical record will be kept for an unknown length of time.

XVIII. Follow-up and Record Retention

The study results will be kept in the subject's research record for at least six years after the study is finished. At that time, the research data that has not been put in the subject's medical record will be destroyed. Any research data that has been put into the medical record will be kept for an unknown length of time.

XIX. Data Safety and Monitoring Plan

Surveillance for medical risks, including but not limited to exacerbation of airway obstruction and respiratory distress, will be performed continuously during the study of each subject by the study investigators. The clinical care team also monitors continuously for exacerbation of airway obstruction and is prepared to intervene immediately.

The Principal Investigator ([name]) will closely oversee the protocol to monitor for any adverse events. Any adverse events will be reported as per IRB guidelines as noted above. Electronic data have several levels of protection. Any file that may contain patient identifiers will be password protected. All computers upon which data are stored are likewise password protected and are running anti-virus programs that automatically update definitions. All data are automatically backed-up to a secondary hard drive on a nightly basis. Access to the Vanderbilt computer network is protected at the level of firewalls, TCP wrappers and university assigned user ID's. Data are secured with encryption algorithms and the network is maintained by the Medical Center's Network Computer Services.

REFERENCES

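### With fixed blocks of 4 in an open-label, clinician-recruited trial, up to one third of allocations on average can be deduced in advance; simple or undisclosed mixed-block randomization would cheaply remove or reduce this.

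*Combined protocol and SAP*

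**What the plan says.** Section II (Summary of Approach): "Treatment allocation (randomization) will be determined by a pre-determined randomization sequence in randomly-permuted blocks of 4". Section VI (Study Procedures) says the same: "The study design will be an RCT with randomization in randomly-permuted blocks of four". Neither section gives a second block size, describes strata, or says that the block size is withheld from anyone.

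On concealment, Section II says: "Envelopes containing treatment allocation by sequential participant ID will be in the VCH-ED charting room", and then: "When a parent and patient provide consent/assent, the next envelope will be opened to determine treatment allocation". On masking: "Treatment allocation cannot be blinded because the vehicle" may itself affect palatability.

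On recruitment, Section V says: "The investigators will be clinicians (attending physicians, fellows, pharmacists, nurses, or nurse practitioners) caring for patients in the VCH ED". They identify eligible children from a convenience sample of 220, and "The investigator will seek written informed consent from the parent and verbal assent from the child".

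Three statements bear on staff preference. The hypothesis in Section I is that crushed tablets "will be more palatable and acceptable in comparison to the IV form of the drug mixed in sugar syrup". Section III reports that nurses prefer the current IV preparation. Section IX claims equipoise.

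**The concern.** With one fixed block size and no strata, the participant ID gives the position within the block. Because treatment is open, staff can see past allocations. A recruiter who knows the block size and the earlier allocations in the current block always knows the fourth assignment, and sometimes the third as well.

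Opening the envelope only after consent and assent stops anyone learning the actual assignment early, but it does not stop deduction from past assignments. Deduction acts earlier, when a clinician decides whether to approach a family and how to present the study. That recruiters have this discretion is inferred from the use of a convenience sample. A child who looks unlikely to take medicine willingly might be approached for one expected arm and passed over for the other, even unconsciously. That difference could carry into the primary outcome, the parent's palatability rating, and appear as a treatment effect.

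**Working it through.** **Inputs from the protocol.** Block size 4 (Sections II and VI); 110 per arm, 220 in total, so 2 + 2 per block and 55 blocks (Sections V and XVI); SD 1.1, difference 0.5, power 0.9, alpha 0.05 (Section XVI). Visibility of past allocations and any rating shift are not in the protocol; the values used below are assumptions.

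**The plan's own figure.** A two-sided two-sample t test with these inputs needs 103 per arm (power 90.09%), as Section XVI states. At 110 per arm power is 91.87%. The protocol gives no figure for predictability.

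**Full tracking.** Of the 6 equally likely orders in a block, 4 have one forced slot and 2 have two.
- Certain share = (4 × 1 + 2 × 2) / (6 × 4) = 8/24 = 33.3%.
- Best guess right = (1/2 + 2/3 + 2/3 + 1) / 4 = 70.8%.
- Blocks with two forced slots follow Binomial(55, 1/3), with 95% range 12-25. Certain allocations therefore number 55 + 12 = 67 to 55 + 25 = 80 of 220 (30.5-36.4%).

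**Partial tracking.** Suppose each earlier in-block allocation is seen independently with probability v and the position is known. The certain share is v²/3.

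| v | Certain | Best guess right |
|---|---|---|
| 1 | 33.3% | 70.8% |
| 0.75 | 18.8% | 64.6% |
| 0.50 | 8.3% | 59.9% |
| 0.25 | 2.1% | 55.4% |

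**What this could do to the test.** Let children approached for expected-tablet and expected-IV slots differ by a shift s. The bias is s × certain share if recruiters act only when certain, and s × (2 × guess rate − 1) if they act on every best guess. The standard error is 1.1 × √(2/110) = 0.148, and the rejection rate under the null comes from the noncentral t with 218 df.

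| Assumption | Full tracking: bias, rate | v = 0.50: bias, rate |
|---|---|---|
| s = 0.25, one direction | 0.083-0.104, 8.7-10.8% | 0.021-0.050, 5.2-6.3% |
| s = 0.25, a quarter of selection reversed (bias halved) | 0.042-0.052, 5.9-6.4% | 0.010-0.025, 5.1-5.3% |
| s = 0.1, one direction | 0.033-0.042, 5.6-5.9% | 0.008-0.020, 5.0-5.2% |

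**Alternatives.**
- *Simple 1:1 randomization.* Nothing can be deduced from past allocations; the best guess is right 50% of the time. Averaged over the binomial split, power is 91.75% at 220 (against 91.87%) and 89.95% at 206 (against 90.09%). At 89 v 117, the edge of the 95% range at 206, it is 89.55%.
- *Blocks of 4, 6 and 8 in random order, with the set of sizes known to the guesser.* By simulation, full tracking gives 2.3% certain and 68.0% of guesses right; v = 0.50 gives 0.02% and 57.8%. With s = 0.25 and action on every best guess, the bias is 0.25 × (2 × 0.680 − 1) = 0.090 and the rate 9.3%, against 10.8% with blocks of 4. At v = 0.50 the rate is 5.8%, against 6.3%. The worst final split, 108 v 112, has power 91.86%.

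**The case against.** The strongest reply is that one third is an extreme case. It needs a recruiter who knows the block size and has seen every earlier allocation in the block. Five staff groups may recruit, and the protocol describes no visible log. The certain share falls with the square of visibility, and independent visibility is itself a simplification; in practice it would cluster by shift and by person. This stands, and one third should be read as an upper bound.

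The harm also rests on stacked assumptions. The 0.25-point shift has no source in the protocol and is half the target difference. Stated preferences point both ways, and evenly opposed selection would average to zero. Dropping either full tracking or the single direction brings the rate to 6.4% or less. This stands too: the documents do not allow the bias to be quantified. Section II also does not say who opens the envelope, or that the nurses who prefer the IV preparation see allocations.

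Neither remedy is perfect. Mixed blocks barely lower best-guess accuracy if the sizes leak. Simple randomization gives up balance over calendar time: the first 110 children could split 45 v 65 (edge of the 95% range), against at most 54 v 56 with blocks of 4 and 53 v 57 with mixed blocks.

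These points limit the weight of the concern. They do not justify keeping one fixed block size, since mixed blocks with undisclosed sizes keep almost all of the balance.

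**Conclusion.** The concern holds as an inexpensive improvement that should be made, with medium confidence as to its practical importance. The fixed block of 4, open treatment and recruitment by treating clinicians are all stated in the protocol. The one-third figure is exact if the block size is known and all earlier in-block allocations are seen; 2-19% of allocations are certain if each is seen with probability 0.25 to 0.75. Any effect on the result depends on an assumed shift, its direction and the degree of tracking. Across the cases examined, the false-positive rate runs from practically 5% to 10.8%, and its upper end needs every assumption to be unfavourable. Bias is possible and avoidable; it is not shown, and its direction is not established. The sample-size calculation is unaffected.

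**What to change.** In Sections II and VI, replace the fixed blocks of 4 with one of the following.

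1. **Randomly mixed block sizes** (for example 4, 6 and 8), with the sizes kept in a document that recruiting clinicians do not see and removed from the protocol text they use. This keeps near-balance at almost no cost in power. It nearly eliminates certain deductions but only modestly reduces informed guessing.
2. **Simple 1:1 randomization** generated in Stata. This is the only option of the two that takes the best guess to 50%. Section XVI should then give 220 in total, with about 110 expected per arm. Its statement that 103 per arm are needed should be reworded, because under Binomial(220, 0.5) one arm falls below 103 in about 31% of lists even without dropouts. Expected power falls by 0.12 percentage points at 220 (0.14 at 206). Per assumed 1 point of linear drift in ratings over the trial, the lost calendar balance adds a chance arm difference with SD √(1/12) × √(4/220) = 0.039 points (0.001 with blocks of 4, 0.005 with mixed blocks), with no bias on average.

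Either option needs new list code, a new set of envelopes and short wording edits. Total sample size, eligibility, outcomes and clinical procedures do not change. The physical security of the envelopes is a separate matter that neither option addresses.

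### Allocation envelopes are kept where the enrolling clinicians work, with no described means of enforcing or checking concealment, in an unblinded trial with a disclosed fixed block size of 4

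*Combined protocol and SAP*

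**What the plan says.** Section II (Summary of Approach) describes a "pre-determined randomization sequence in randomly-permuted blocks of 4, to be generated using Stata statistical software". It then gives the mechanism and its location: "Envelopes containing treatment allocation by sequential participant ID will be in the VCH-ED charting room where physicians and nurse practitioners enter orders". On timing it says: "When a parent and patient provide consent/assent, the next envelope will be opened to determine treatment allocation". The next step is: "The clinician will then enter the order for dexamethasone tablets or IV solution in accordance with this". The same section states that treatment cannot be blinded.

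Section V (Subject Recruitment and Enrollment) says who recruits: "The investigators will be clinicians (attending physicians, fellows, pharmacists, nurses, or nurse practitioners) caring for patients in the VCH ED". It also says: "The investigator will seek written informed consent from the parent and verbal assent from the child". The sampling is by convenience: "We will enroll a convenience sample of 220 children 1-7 years of age and their parent".

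Section VIII (Outcome Variables) makes the primary outcome a smiley-face palatability score completed by the parent. Section XIII (Data Management) says "All data will be entered in a secure REDCap database" and does not connect that database with randomization.

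No section says whether the envelopes are sealed or opaque, who holds them, who opens them, or whether openings are logged or checked.

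**The concern.** Concealment protects the step between deciding to approach a child and learning that child's arm. In this plan one group of staff covers the whole chain: treating clinicians pick the child, seek consent and place the order, and the envelopes are in a room they use for ordering. A clinician who learned or guessed the next arm could approach a cooperative child now or wait for another. Convenience sampling would leave no trace of that choice.

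The outcome is sensitive to such a choice. A young child's cooperativeness is visible before enrolment and could plausibly affect a parent's unblinded rating. No baseline measure of it is listed, so the analysis could not reliably repair an imbalance. Preferences also exist. Section III reports that nursing staff favour the current IV preparation in syrup, and nurses are among the listed investigators, while the study hypothesis favours the tablet.

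There are two separate routes to knowing the next arm. One is deduction from past assignments, which depends on the block scheme. The other is looking at an envelope early, which depends on custody and which no block scheme prevents.

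**Working it through.** **Inputs from Section XVI (Sample Size).** Target difference 0.5, SD 1.1, type I error 0.05, power 0.9, 103 per arm needed, 110 per arm enrolled (220 in total). From Section II: 1:1 blocks of 4, unblinded.

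**The plan's own figure.** Normal approximation, two-sided: n = 2 × (1.960 + 1.282)² × 1.1² / 0.5² = 101.7, rounded up to 102. The two-sided t-test gives 102.7, rounded up to 103. The stated 103 reproduces, and this point does not change it.

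**Deduction from past assignments.** A block of 4 with two of each arm has 6 equally likely orders.
- In 2 of the 6 (AABB, BBAA) the third and fourth assignments are determined by the earlier ones. In the other 4 only the fourth is.
- Determined assignments: 2 × 2 + 4 × 1 = 8 of 6 × 4 = 24, or 33%. Over 220 children that is about 73.
- Best guessing succeeds with probability 1/2, 2/3, 2/3 and 1 at positions 1 to 4. The mean is 2.833/4 = 70.8%, about 156 of 220, against 50% by chance.

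These figures require knowledge of every earlier assignment and of where each block starts, so they are upper bounds.

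**Illustrative effect of steering.** The documents give no steering rate and no gain in score from steering, so both are assumed here. Bias = share steered × gain in score, doubled if both arms are steered in opposite directions. SE of the difference = 1.1 × √(2/103) = 0.153. Two-sided rejection under the null = Φ(−1.96 + bias/SE) + Φ(−1.96 − bias/SE).

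| Assumed steering | Bias (points) | Type I error |
|---|---|---|
| 5% of one arm, 0.5-point gain | 0.025 | 5.3% |
| 5% of both arms, opposite directions, 0.5 | 0.05 | 6.2% |
| 10% of one arm, 1 point | 0.1 | 10% |
| 10% of both arms, opposite directions, 1 point | 0.2 | 26% |

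A 1-point gain is about 0.9 SD (1/1.1), so the last two rows are demanding assumptions.

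**The case against.** The plan is not without safeguards. Envelopes follow participant ID in sequence, and the next one is opened only after consent/assent. Sections V and VI keep the same order: consent, enrolment, then allocation. Followed as written, that conceals the assignment until the child is in the trial. Silence on sealing and opacity may only be brevity in a short protocol. The 33% needs complete knowledge of past assignments, which is hard when enrolment is spread over many clinicians. The steering scenarios are assumed, and at the mild end the type I error hardly moves. The stated preference belongs to nursing staff, whereas the charting room is described as used by physicians and nurse practitioners. Because the hypothesis favours the other arm, the direction of any steering is unclear.

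Most of this stands, and it limits how the point may be put. A reader might infer that the enrolling clinicians open the envelopes themselves and that all assignments are in effect visible to them. The documents do not support that. The sentence on opening is passive and names no one, and knowledge of 100% of assignments would require every envelope to be inspected, which nothing in the text reports. A reader might also infer that REDCap is ready to release allocations. It is documented for data entry only.

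The objection does not remove the exposure created by the stated arrangement. The consent-first rule is an instruction. The envelopes are placed with staff who choose whom to approach, and no custodian, log or check is described that would prevent or reveal a departure.

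**Conclusion.** The point holds as a weakness in the stated method of concealment, and it should be corrected before enrolment. It is not a finding that concealment has failed. What the documents establish is the location of the envelopes, the overlap between treating, selecting and consenting staff, the open treatment, the parent-rated outcome and the disclosed block size of 4. What they leave open is who opens the envelopes and how these are secured.

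The only size that follows from the design itself is the ceiling of 33% of assignments deducible with certainty, given full knowledge of earlier assignments and block boundaries. The type I error range, from about 5% to 10% with one arm steered and 26% with both arms steered in opposite directions, shows what could be at stake. It rests wholly on assumed steering rates and gains, with SD 1.1 and 103 analysed per arm. It is not an estimate of what will happen in this trial.

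**What to change.** In Section II, replace the charting-room envelopes with allocation that is released only after consent and eligibility have been recorded for that child. Two routes would serve:

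- The trial's REDCap database, if its set-up allows. This has to be confirmed, including access for the enrolling clinicians, because Section XIII describes it for data entry only.
- Otherwise, sealed, opaque, numbered envelopes held by someone not involved in enrolling, such as a study pharmacist who does not enrol, with an opening log. Pharmacists are among the investigators listed in Section V, so the protocol should state that the holder does not recruit. Better envelopes left in the charting room would only supply missing detail, since custody would not change.

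In either case, generate the Stata list with randomly varying block sizes and do not disclose them to enrolling clinicians. Sections II and VI should no longer state the size. Loading the present list into a new system would leave the 33% unchanged.

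Sample size, eligibility, treatments and outcomes are unaffected. The cost is a new list before the first child and one short step before each order.

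### As described, the face scale is explained to the parent by an investigator who already knows the arm, with no fixed wording and no provision for explaining it before allocation

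*Combined protocol and SAP*

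**What the plan says.** Section II (Summary of Approach) sets out the steps in order. Consent comes first, and then: "When a parent and patient provide consent/assent, the next envelope will be opened to determine treatment allocation". The clinician next enters the order for the allocated preparation. The following sentence reads: "The clinician will ask the participant's parent to complete the data collection form (enclosed with this application) 1-hour after medication administration".

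Section VI (Study Design) follows the same order: "After participant enrollment and ascertainment of treatment allocation (randomization), the clinician will order dexamethasone accordingly in tablet or IV form". The next sentence is: "The investigator will provide the parent with the study data form and instruct the parent in completion of this form 1-hour after dexamethasone administration".

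Four other statements bear on the point:

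- Section V, on who does this work: "The investigators will be clinicians (attending physicians, fellows, pharmacists, nurses, or nurse practitioners) caring for patients in the VCH ED".
- Section II, on blinding: "Treatment allocation cannot be blinded because the vehicle (apple sauce, pudding or sugar syrup) may be associated with palatability and acceptability".
- Section VIII, which defines the outcome as palatability on a 5-point face scale that the parent completes. Section XV adds that the parent's mark is read as a continuous value. Section II also mentions a questionnaire but does not describe its content.
- Section III, on the current IV preparation: "Our nursing staff prefers this preparation". The hypothesis in Section I favours the tablets.

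The supplied text contains no script or standard wording for the explanation, no statement that it comes before allocation, and no provision for it to be given by someone unaware of the arm.

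**The concern.** The primary outcome is a single proxy judgement by a parent about a child aged 1 to 7 years, so what the parent is told about the scale can affect where the mark goes. If the person explaining it knows the arm, emphasis or examples may differ between arms without anyone intending it. Such a difference would add to, or subtract from, the treatment difference. Nothing in the plan records what was said, so it could not be adjusted for afterwards, and enrolling more children would not dilute it.

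The plan's reason for not blinding does not cover this step. The vehicle makes the preparation obvious once it is given. That does not require the scale to be explained after the envelope has been opened. This route to bias can be closed in an otherwise open trial.

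**Working it through.** **Order of steps.** Setting Sections II and VI side by side:

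| Step | Section II | Section VI |
|---|---|---|
| 1 | Consent/assent | Enrolment |
| 2 | Envelope opened | Allocation ascertained |
| 3 | Clinician orders the allocated preparation | Clinician orders the allocated preparation |
| 4 | Clinician asks parent to complete the form at 1 hour | Investigator gives parent the form and instructs them |

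Both accounts place the form after the allocation. In Section II the clinician who enters the arm-specific order also asks for the rating.

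**Inputs for the illustration (Section XVI).** SD 1.1, difference 0.5, power 0.9, type I error 0.05, 103 per arm needed, 110 per arm enrolled. Sidedness is not stated.

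**The plan's own figure.** With a two-sided test and the normal approximation, n per arm = 2 × (1.960 + 1.282)² × 1.1² / 0.5² = 101.7, which rounds up to 102. The two-sample t-test gives 102.7, which rounds up to 103 and matches the plan. A one-sided normal calculation gives 83, so the plan's figure corresponds to a two-sided test.

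**Standard error of the difference.** SE = 1.1 × √(2/103) = 0.153.

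**False-positive rate under a spurious shift b with no true difference.** The rejection probability is Φ(b/SE − 1.960) + Φ(−b/SE − 1.960).

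- b = 0: 0.05.
- b = 0.1: b/SE = 0.652; Φ(−1.308) + Φ(−2.612) = 0.10.
- b = 0.2: b/SE = 1.305; Φ(−0.655) + Φ(−3.265) = 0.26.

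**Power when the shift opposes a true difference of 0.5.** Power is Φ((0.5 − b)/SE − 1.960).

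- b = 0: 0.90.
- b = 0.1: Φ(0.4/0.153 − 1.960) = 0.74.
- b = 0.2: Φ(0.3/0.153 − 1.960) = 0.50.

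**At full enrolment.** With 110 per arm, SE = 1.1 × √(2/110) = 0.148, and the false-positive rates for shifts of 0.1 and 0.2 are 0.10 and 0.27. A larger sample makes a fixed shift slightly easier to mistake for an effect.

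The shift sizes are assumptions; the documents contain nothing from which to estimate them. They are in the same points as the SD of 1.1. For scale, 0.1 is one fifth of the planned difference (0.1/0.5).

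**The case against.** The timing is an inference. No sentence says that the instruction is given only after allocation. In Section VI the 1-hour phrase can attach to completing the form rather than to the instruction, and the form sentences carry no explicit link to the envelope. A site could hand over the form at consent without contradicting the text. This stands to the extent that a reader should not take the plan to forbid earlier instruction. The order of steps in both sections still points to later instruction, and nothing provides for it earlier.

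The data form was enclosed with the application and is not in the supplied text. It may already carry printed instructions, so one cannot conclude that parents receive no standard wording. Printed wording would reduce the risk but not remove it, because Section VI still calls for personal instruction.

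A reader might also infer that staff will steer parents. The documents do not support that. The protocol speaks of instructing, not of persuading. The nurses' preference is stated without a reason and need not be about taste; the sentence after it notes that some children spit the preparation out or vomit. Section IX states equipoise. The recorded leanings run in both directions and could partly cancel, whereas the illustration assumes a consistent net shift. All of this stands: the text shows an open route, not a known bias or its direction.

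Finally, earlier instruction would not stop a remark about the drug made at ordering, at dosing or during the following hour, and the parent will know the preparation when marking the scale. That also stands, and it limits what the change can achieve.

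**Conclusion.** The point holds as an avoidable design weakness. Sections II and VI, as written, describe an unblinded treating investigator explaining a subjective primary rating after the arm is known, and the plan neither moves that explanation ahead of allocation nor fixes its wording.

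Its actual size is unknown. The 10% to 26% false-positive range is illustrative. It rests on assumed net shifts of 0.1 to 0.2 points, 103 evaluable children per arm, SD 1.1 and a two-sided test at 0.05. Any bias of that size would give the same figures, so they are not evidence about this particular route.

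Three stronger readings are not supported: that the protocol requires instruction only after allocation, that biased instruction will occur, and that reordering would remove open-label bias. Section II also mentions a questionnaire, so the face scale is the only measure named in the definition of palatability in Section VIII, but not necessarily the only item that the parent completes. The change is worth making because it is cheap and leaves the sample size untouched.

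**What to change.** In Sections II and VI, state that after consent and before the envelope is opened the investigator hands over the data form and explains the face scale. The explanation should follow one short neutral script that mentions neither the hypothesis nor which preparation is standard. Print the script on the form if it is not already there. At 1 hour, staff only prompt the parent, who marks the form unaided.

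The cost is reordering one step and writing a few lines of text. The same staff and form are used, and the 1-hour rating time and the sample size do not change. The small downside is that the parent must recall the explanation at 1 hour, which the printed wording covers. The protocol should also acknowledge that bias from the parent's and staff's knowledge of the preparation remains.
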